This will be a single-center, blinded, randomized, placebo-controlled,

parallel–group, single-dose, dose-escalation, comparison study investigating safety, tolerability, and PK of emodepside, after administration as fasted or fed doses of oral liquid service formulation (LSF) or immediate release (IR) tablets in healthy male subjects. Optionally, a single dose of a 5 and 20 mg IR tablet formulation will be tested subsequently to the completion of the respective dose steps of the single-dose escalation with oral solution.

Because emodepside has never been given to humans before, the first dose will be staggered. Two leading subjects will be dosed no later than the day before the remaining subjects in Cohort 1 will be dosed. To maintain the blind nature of the study, it will be ensured that 1 of the leading subjects, and 1 of the remaining subjects, are randomized to receive placebo.

The study will be performed in a single site specialized in Phase 1 studies. For each subject the study starts with the Screening Visit, which can be up to 4 weeks before the profile day (dosing). Subjects who participate in Cohort 10, will attend a second Screening visit for ophthalmology assessments, if all other screening assessments show that they're suitable.

For eligible subjects, admission to the ward will be at latest the evening before the Pre-Day. One dose step per subject consists of one Pre-Day, one Profile Day and an in-house observation period of 7 days after administration of test substance. Subjects will be discharged from the study ward 7 days after administration of test substance provided there are no medical objections (Day 7) (Follow-Up Option 1).

However, if it is observed that mean half-life of emodepside in any previous cohort is longer than expected from the preclinical PK of 36 hours, and plasma concentrations of emodepside are still present 7 days after dosing, 2 alternative options may be employed to follow subjects after Day 7 (Figure 2) from Cohort 5 onwards and for all subjects in subsequent cohorts (this decision will be made during the Safety Review Meetings):

- Option 2: addition of up to 4 out-patient follow-up visits with measurements for safety and blood samples for PK over a period up to an additional 14 days (ie, up to Day 21); or
- Option 3: prolongation of the in-house period of up to an additional 7 days (ie, up to Day 14) with additional measurements for safety and blood samples for PK on up to 4 days during that period

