In all cases, approximately three weeks after their dose of study medicine (Day 21) the subjects will undergo their final examinations in a Follow-Up Visit. In Part 2, Cohorts 9 and 10 will follow Option 2. The out-patient visits for Cohort 9 will be decided at the dose decision meeting for that cohort. Cohort 10 will have out-patient visits on Days 10, 14 and 18.

Rationale for Study Design

This study applies a standard Phase I single dose escalation design. The data from this Single Ascending Dose study will be used to design subsequent Phase I studies of emodepside (eg, additional food effect and multiple ascending dose studies).

The study is performed in a blinded design, in which the subjects and the study personnel (investigators and nurses) are blinded. The decision about dose escalation will be taken in the Safety Review Meeting prior to each new dose step (see 'Safety Review' section.)

The rationale for the starting dose, and selection of study population are

covered in the section "Rationale of study design and dosing".

The rationale for the 7 day in-house period is based on an assumed dominant half-life of emodepside of 36 hours, derived from pharmacokinetics in dog and rat after oral administration. Applying the convention of in-house stay corresponding to 5 half-lives: $36h \times 5 = 180h$, equivalent to 7.5 days. However this may be extended if subjects have relevant plasma concentrations in early dose steps.

Main Entry Criteria

Inclusion:

- Male, Caucasian volunteers, deemed healthy on the basis of a clinical history, physical examination, ECG, vital signs, and laboratory tests of blood and urine. Optionally, after further evaluation during the study, at the sponsor's discretion other ethnic groups may be recruited.
- 18 to 55 years of age
- Normal body weight (BMI; Quetelet index) in the range of 18 and 30.1 kg/m² at screening
- Sufficient intelligence to understand the nature of the trial and any hazards of participating in it. Ability to communicate satisfactorily with the investigator and to participate in, and comply with the requirements of, the entire trial.
- Willingness to give written consent to participate, after reading the information and consent form, and after having the opportunity to discuss the trial with the investigator or his delegate
- Willingness to give written consent to have data entered into The Overvolunteering Prevention System

Exclusion:

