1.4. Assessment and Management of Risk

Emodepside has never been given to humans before, so a sentinel dosing approach will be used at the first dose level. The dose in Cohort 1 will first be given to 2

sentinel subjects and the remaining subjects will not be dosed until at least 23 h later following review of available safety and tolerability data. To maintain the blinded nature of the study, the sentinel subjects will be randomized in a 1:1 ratio to receive emodepside:placebo.

Subjects in the FiH study (Part 1, Cohorts 1-8) and part 2 cohort 9, will remain hospitalized and will be closely monitored during the 7 days after their dose. A Safety Review Group (SRG) will be set-up to review any safety signal.

Part 2, Cohort 10:

The previous version of the protocol (version 4.0, dated 05 October 2016) included an additional optional cohort (Cohort 10). This cohort will be included, in order to explore in detail the effect of emodepside on the eye system using a dose level that was already completed in a prior cohort (see Section 1.3). Therefore this cohort is exploratory in nature, and is not considered to be FIH because it will repeat a dose level already tested in Part 1 of the study. Subjects will be transported to an eye hospital for ophthalmology assessments approximately 2-2.5 h post-dose and then transported back to the phase 1 unit, otherwise subjects will remain hospitalized in the phase 1 unit for 7 days consecutively following the single dose. Subjects could potentially be off-site (at the eye hospital) during or after the expected T_{max} , however they will be under the direct medical supervision of a physician and nurse from the phase 1 unit at all times (including transportation). A dose of 40 mg LSF solution was previously tested in Part 1, Cohort 8, and the safety and tolerability profile was found acceptable.

As Part 1 of this study is considered FIH, before a subject can be dosed in Part 1 (Cohorts 1-8) a General Practitioner (GP) reply must be obtained, or a valid GP reply must be on file.

As the doses to be tested in Part 2 (Cohorts 9 and 10) will have already been tested within this study; those cohorts are not considered FIH. For those cohorts, subjects' GPs will be contacted but a reply is not required prior to dosing.

Any safety risk to study participants is mitigated by the following considerations:

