Emodepside is registered as veterinary product worldwide. Therefore, a complete toxicological package is available which also covers human requirements.

It is shown in a set of genotoxicity studies that emodepside is not genotoxic. Additionally, developmental toxicity studies in rats and rabbits showed that emodepside had no teratogenic or primary embryo/ fetotoxic potential. However, contraception will be used during the study in accordance with MHRA request and HMR standard procedures (see Section 4.3 on Dietary and Lifestyle Guidelines).

Based on the nonclinical safety data, the toxicological release conference gave the following recommendations for the first in men study:

The recommended starting dose in humans (70kg) is 1.75 mg/day.

- Monitoring of standard parameters, including blood pressure, glucose homeostasis (glucose, insulin, glucagon). Increased glucose levels and decreased insulin and glucagon levels have been observed in the non-clinical safety studies.
- Once the dose escalation is approaching plasma concentrations which were pre-clinically associated with CNS effects, particular attention should be given to observations/investigations indicating prodromal signs of tremor and incoordination.
- Due to missing data on phototoxicity clinical trial participants should avoid exposure to excessive sunlight
- Strong CYP3A4 inducers and inhibitors as well as co-medications that are relevant substrates for CYP3A4 should be excluded or closely monitored until the drug-interaction potential has been assessed in more detail.
- Strong P-gp inhibitors as well as co-medications that are relevant substrates for P-gp should be excluded or closely monitored until the drug-interaction potential has been assessed in more detail.
- The potential of emodepside to inhibit CYP3A4 and P-gp has to be further assessed clinically once it becomes clearer which emodepside exposure will be achieved at the therapeutic dose in humans.

The NOAEL of emodepside in dogs was $AUC_{(0-24)}$ 860 μ g·h/L, C_{max} 175 μ g/L, after 1 week at a dose level of 5 mg/kg. This dose resulted in an exposure after 4 weeks of $AUC_{(0-24)}$ 1611 μ g•h/L, C_{max} 238 μ g/L.

The maximal dose tested in dogs was 20 mg/kg. This dose resulted in an exposure after 4 weeks of AUC₍₀₋₂₄₎ 15887 μg•h/L, C_{max} 1682 μg/L.

(Note: The recommended starting dose in humans (70kg) is 1.75 mg/day, however for technical reasons (see Section 3.3) the dose of 1.0 mg is chosen as the starting dose)

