The study will be performed in a single site specialized in Phase 1 studies. For each subject the study starts with the Screening Visit, which can be up to 4 weeks before the profile day (dosing). For eligible subjects, admission to the ward will be at latest the evening before the Pre-Day (Figure 2). One dose step per subject consists of one Pre-Day, one Profile Day and an in-house observation period of 7 days after administration of test substance.

Subjects will be discharged from the study ward 7 days after administration of test substance provided there are no medical objections (Day 7) – "Option 1" in Figure 2.

Figure 1- Study Design Overview

[figure not shown]
[figure not shown]

Figure 2- Parts 1 and 2: Study Flow Chart - Subject Level

* Follow-Up Visit = 3 weeks post-dose (Day 21)

*If eligible for study entry based on Screening Visit 1, subjects to be included in Part 2 Cohort 10 will have a second Screening Visit in order to undergo an ophthalmology assessment (within 7 days prior to Profile-Day [Day 0]) or on Pre Day at the latest.

However, if it is observed that **mean half-life of emodepside in any cohort** is longer than expected from the preclinical PK, and plasma concentrations of emodepside are still present 7 days after dosing, 2 alternative options may be employed to follow subjects after Day 7 (Figure 2) from Cohort 5 onwards and for all

subjects in **subsequent cohorts** (this decision will be made during Safety Review Meeting(s) – Section 11):

- Option 2: addition of up to 4 out-patient visits with measurements for safety and blood samples for PK over a period up to an additional 14 days (ie, up to follow-up on Day 21); or
- Option 3: prolongation of the in-house period for up to an additional 7 days (ie, up to Day 14) with additional measurements for safety and blood samples for PK taken on up to 4 days during that period.

Cohort 9 will follow option 2, (up to 4 visits during the period from Day 8–21 inclusive, as needed) and Cohort 10 will have outpatient visits on Days 10, 14 and 18.

In all cases, approximately three weeks after their dose of study medicine the subjects will undergo their final examinations in a Follow-Up Visit.

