3.3. Rationale of Study Design and Dosing

This study applies a standard Phase I single dose escalation design. The data from this Single Ascending Dose study will be used to design subsequent Phase I studies of emodepside (eg, additional food effect and multiple ascending dose studies.)

The study will be performed in healthy male Caucasian volunteers. Currently there are no data to indicate that emodepside will be sensitive to ethnic factors, according to criteria in ICH Guideline E5 'Ethnic Factors in the Acceptability of Foreign Clinical Data'. As per the ICH E5 guidelines, knowledge of the pharmacokinetic and pharmacodynamic properties, and the translation of these to clinical efficacy and safety, are required to assess if emodepside will be sensitive to ethnic factors. Therefore data gathered in the current study will contribute to an evaluation of the need for a bridging study in other ethnic groups. However optionally, after further evaluation during the study, at the sponsor's discretion other ethnic groups may be recruited.

The study is performed in a blinded design, in which the subjects and the study personal (investigators and nurses) are blinded, in order to avoid bias in the collection and evaluation of data in its conduct. Placebo has been chosen as the control treatment to assess whether any observed effects are treatment-related or simply reflect the study conditions.

The decision about dose escalation will be taken in the Safety Review Meeting, prior to dosing of the subsequent cohort (see Section 7.4).

The rationale for the 7 day in-house period is based on an assumed dominant half-life of emodepside of 36 hours, derived from pharmacokinetics in dog and rat after oral administration. Applying the convention of in-house stay corresponding to 5 half-lives: $36h \times 5 = 180h$, equivalent to 7.5 days. However this may be extended if subjects have relevant plasma concentrations in early dose steps.

The 7 day Follow-Up Visit is scheduled according to standard practice for this type of study.

The recommended starting dose in humans (70 kg) was calculated to be 1.75 mg/day (0.025 mg/kg), based on the following data:

- 28 days rats study: No Observed Adverse Effect Level (NOAEL) = 5 mg/kg
 ► Human Equivalent Dose (HED) + safety factor 10 = 0.082 mg/kg
- 28 days dog study: NOAEL = 5 mg/kg ➤ HED + safety factor 10 = 0.27 mg/kg

Dosages resulting in Margins of Safety of 10 from predicted human PK (unbound C_{max} from dog scenario):

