Subjects must not expose themselves to sunlight (eg go out of doors) for longer than 15 minutes without using a strong sunblock (sun protection factor (SPF) 30 or above), or use a sunbed, or expose themselves to other sources of UV light, while they are taking emodepside and until 3 days after their last dose.

According to HMR standard procedures, and MHRA request, during the study and until 90 days following dosing, subjects must not have sex without using a condom, unless they have had a vasectomy or their partner is not of childbearing potential.

Part 2, Cohort 10

Subjects will be informed that they will need to bring their distance glasses (if applicable) to ophthalmology assessment visits. Also, their near vision will be blurred for approximately 2 hours (due to the use of mydriatic eye drops) following the eyetesting procedures at Screening Visit 2. Therefore subjects will not be able to drive or operate machinery afterwards for at least 2 hours. On Profile-Day (Day 0), the ophthalmology assessments will be repeated post-dose, but without the use of mydriatic eye drops.

5. Schedule of Events

Table 3. Schedule of Events (Part 1, Cohorts 1-8, and Part 2, Cohort 9)

Study Procedure	Screen			In-Patient Phase									sea																		Follow-						
,	Visit						Pre	-Day	,									Pro	file-	Day								Eva	luat	ion			Se	e Ta	able 4	t _o	Up
Day ± allowable deviation	-28 to -2	-2					•	-1											0						,	1	2	3	4	5	6	7					7 +3
Subject information and Informed Consent	Х																																				
Medical history (including demographics and previous / concomitant medications)	Х																																				
Physical examination ^c	Х																																				Χ
Neurological examination ^d	Х																																				Χ
Ward Admission (approx.16h)		Χ																																			
Urine drugs of abuse and alcohol breath test	Х	Х																																			
Hours ^a (pre/post drug)		-36	-24*	-23.5	-23	-22.5	-22	-21	-20	-18	-16	-12	0*	0.5	1	1.5	2	2.5	3	4	5	6	8	12	24	36	48	72	96	120	144	168					
Glucose, Insulin, Glucagon, and Cortisol profiles			Х		Х		Х		Х			Х	Х		Х		Х			Х				Х	Х												
Samples for Prolactin & Leptin			Χ										Х												Х												
Administration of emodepside ^e													Х																								
12-lead safety ECG ^f	Х		χ [†]	Χ	Х	Χ	Χ	Χ	Χ		Χ	Χ	χ [†]	Χ	Χ	Χ	Χ		Χ	Χ			Χ	Χ	Χ		Χ	Χ	Χ	Χ	Χ	Χ					Χ

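### The sunlight/UV precaution ends on Day 3, while subjects are still on the ward, so it covers none of the time at home before Follow-Up and is not lengthened under Option 2 or 3 (minor; cheap to improve)

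*Protocol*

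**What the plan says.** Protocol Section 1.4 gives the reason for the precaution: "Due to missing data on phototoxicity clinical trial participants should avoid exposure to excessive sunlight". That recommendation has no end date.

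Section 4.3, repeated in the Protocol Summary under the entry criteria, turns it into a rule. Subjects may not spend more than a quarter of an hour in sunlight without high-factor sunblock, use a sunbed, or be exposed to other UV sources, "while they are taking emodepside and until 3 days after their last dose".

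The ward stay is longer. Section 3.1 states: "Subjects will be discharged from the study ward 7 days after administration of test substance". Section 3.3 bases that stay on an assumed 36 h half-life, "Applying the convention of in-house stay corresponding to 5 half-lives", and lets it adapt: "However this may be extended if subjects have relevant plasma concentrations in early dose steps".

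Follow-up adapts too. The Protocol Summary allows Option 2 (extra out-patient visits) or Option 3 (a longer stay, to Day 14 at most) if the mean half-life in an earlier cohort is "longer than expected from the preclinical PK of 36 hours, and plasma concentrations of emodepside are still present 7 days after dosing". It then says: "In Part 2, Cohorts 9 and 10 will follow Option 2". Section 8.10 fixes Cohort 10's out-patient visits, with PK samples, on Days 10, 14 and 18.

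Two other restrictions in Section 4.3, on grapefruit and on strenuous exercise, last until after the Follow-Up Visit.

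**The concern.** The precaution is there because a hazard has not been tested, and it is needed most when the unit no longer controls where the subject spends the day. As written, it ends four days before a Day 7 discharge.

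The ward stay and the follow-up schedule both respond to slow elimination; the UV rule does not. A cohort can be followed to Day 21 because drug is expected to persist, yet its sun precaution still stops on Day 3. The available text gives no reason for choosing 3 days.

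If elimination in humans is slower than assumed, subjects could go home with drug on board, an unknown phototoxic potential and no sun restriction in the protocol.

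**Working it through.** **Inputs.** Single dose on Day 0. UV rule to 3 days after dosing (Section 4.3). Discharge on Day 7 under Options 1 and 2, or up to Day 14 under Option 3 (Section 3.1). Follow-Up at 3 weeks (+3 days) (Sections 3.2 and 8.11). Assumed half-life 36 h (Section 3.3). The Table 3 follow-up column and one sentence in Section 3.3 point to a 7-day follow-up. Sections 3.1, 3.2 and 8.11 and Table 5 all give three weeks, and that is used here.

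**The plan's own figure.** 5 × 36 h = 180 h = 7.5 days. This reproduces Section 3.3. It falls 180 − 168 = 12 h after a Day 7 discharge.

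**Days at home covered by the rule.**

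| Discharge | Days at home to Follow-Up | Days covered |
|---|---|---|
| Day 7 (Options 1, 2) | 21 − 7 = 14, to 24 − 7 = 17 | 0 |
| Day 14 (Option 3, latest) | 21 − 14 = 7, to 24 − 14 = 10 | 0 |

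**Fraction remaining**, from 0.5^(t / half-life), assuming mono-exponential decline:

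| Half-life | At 72 h (rule ends) | At 168 h (discharge) |
|---|---|---|
| 33 h (low end of animal range, Section 1.2) | 22% | 2.9% |
| 36 h (protocol assumption) | 25% | 3.9% |
| 43 h (high end of animal range) | 31% | 6.7% |
| 72 h (illustration only) | 50% | 20% |
| 100 h (illustration only) | 61% | 31% |

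At 36 h, 72 h is 72/36 = 2 half-lives. More than 10% remains at discharge only if the half-life exceeds 168 × ln 2 / ln 10 = 50.6 h.

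**Ceiling on late plasma levels.** Section 1.3 reports for Cohort 8 (40 mg solution) a mean Cmax of 612 ng/mL and an AUC of 4315 ng.h/mL. Suppose that AUC, A, runs to infinity and the terminal phase is at most k·A·exp(−kt). Its largest possible value at time t, reached at k = 1/t, is A/(e·t):

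- at 72 h: 4315 / (2.718 × 72) = 22 ng/mL, 3.6% of Cmax
- at 168 h: 4315 / (2.718 × 168) = 9.4 ng/mL, 1.5% of Cmax

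The AUC type is not stated. If it is a partial AUC, this ceiling does not apply.

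**Who is left.** Section 1.3 counts 71 subjects given emodepside or placebo, 63 of them in Cohorts 1 to 8. The other 71 − 63 = 8 fit Cohort 9. That leaves Cohort 10: up to 8 subjects, 6 on 40 mg, the highest dose.

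**The case against.** The strongest reply is that no harm is documented. At 36 h little drug is left at discharge, and the available text gives no human half-life (part of Section 1.3 is missing from it). Any excess over 36 h, with drug still detectable, meets the Option 2 trigger, so choosing Option 2 does not show a relevant level. If the reported AUC is to infinity, plasma is already low when the rule ends. All of this stands, and it keeps the point small. Two things limit it. The ceiling depends on an unstated AUC type. It also concerns plasma only: Section 1.2 reports higher concentrations in rat tissues than in blood, and Section 3.3 predicts a human volume of distribution of 11 to 15 L/kg. Skin levels are not reported.

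Existing cover also counts. Days 0 to 3 include peak exposure and the Cohort 10 trip ("Subjects will be transported to an eye hospital for ophthalmology assessments approximately 2-2.5 h post-dose"). Section 8.9 allows recall to the ward for unexpectedly high plasma levels. Adverse events are asked about on Days 10, 14, 18 and 21 in Cohort 10, and the available text reports no phototoxic event. None of this restores the precaution at home, but slow elimination would not go unwatched.

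The comparison with grapefruit and exercise is imperfect, because both restrictions start before dosing and so are not purely about residual drug. They show that the end point is workable, not that it is pharmacologically required.

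A reader might infer that 3 days breaks the protocol's five-half-life convention. It does not: Section 3.3 states that convention for the in-house stay only. A reader might also infer that subjects go home with no sun advice at all. That cannot be established, since the house rules, the Study Procedures Manual and the information sheet are not available.

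**Conclusion.** The point holds, at low severity. The day count is certain: the precaution covers none of the time at home under any option, and no available text lengthens it when drug persists. The figure of 14 to 17 days belongs to a Day 7 discharge; under Option 3 the period can be as short as 7 to 10 days.

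Whether the gap matters depends on a quantity the available text does not give. At 36 h it is minor. It becomes material only with a longer human terminal half-life, which placing Cohorts 9 and 10 on Option 2 suggests but does not prove. At most about 6 subjects on active drug, each given one dose, stand to benefit. The case for change is that the rule does not follow the protocol's own handling of persisting drug and that correcting it is cheap.

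**What to change.** In the Protocol Summary, Section 4.3 and the Cohort 10 information sheet, change the end of the sunlight/UV restriction from 3 days after the last dose to *until after the Follow-Up Visit*.

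If the sponsor wants a shorter period, it should be five times the terminal half-life observed in Part 1, with that value stated, and no less than 7.5 days. At 36 h this would add only 12 h at home.

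Cost: one sentence in two places of the protocol, plus the information sheet. Up to 8 remaining subjects (6 on active drug) would use sunblock or limit sun and sunbeds for about 14 to 17 more days at home. There is no added visit, sample or analysis. Under Sections 6, 13 and 15 the revised information sheet and protocol text may need ethics approval and, if the amendment is substantial, regulatory approval before use.
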